4. STUDY ASSESSMENTS

4.1 CROHN'S DISEASE ACTIVITY INDEX (CROHN'S DISEASE PATIENTS)

The Crohn's Disease Activity Index (CDAI) consists of the following 8 items: abdominal pain, number of liquid stools, general well-being, extraintestinal complication, use of antidiarrheal drugs, abdominal mass, hematocrit, and body weight. Information on abdominal

pain, general well-being, and frequency of loose and watery stools will be taken from a daily diary completed by the subject.

Total CDAI scores can range from 0 to approximately 600 with higher scores indicating more active disease. Disease severity as measured by CDAI is categorized as: Remission (<150), Mildly active disease (150 - 219); Moderately active disease (220 - 450); Severe disease (> 450).

Item and total scores, as outlined below, will be derived programmatically for Visit 1 (Screening), Visits 2 (Day 0), 4 (Day 14), 6 (Day 28), 8 (Day 42), and Visit 10 (Day 56/ET).

The CDAI total score consists of 8 item scores:

- 1) The liquid stools score is calculated as the sum of the number of loose/watery stools values recorded for the 7 days prior to the visit;
- 2) The abdominal pain score is calculated as the sum of the abdominal pain values recorded for the 7 days prior to the visit. Abdominal pain severity (graded from 0 3 with higher values indicating greater severity) summed over the previous 7 days, where 0 = "None", 1 = "Mild", 2 = "Moderate", 3 = "Severe";
- 3) The general well-being score is calculated as the sum of the general well-being values recorded for the 7 days prior to the visit. General well-being is graded from 0 4 with higher values indicating a poorer condition of health, where 0 = "Generally well", 1 = "Slightly under par", 2 = "Poor", 3 = "Very poor", 4 = "Terrible";
- 4) The extraintestinal complications score is calculated as the number of complications present (0 to 6) from the following list:
 - Arthritis/arthralgia
 - Iritis/uveitis
 - Skin/mouth lesions
 - Peri-anal disease
 - Other fistula
 - Fever >37.8 °C, >100 °F (in the last week);
- 5) Taking medication for symptomatic relief from diarrhea (0 = No, 1 = Yes);
- 6) Presence of an abdominal mass (0 = None, 2 = Questionable, 5 = Definite);
- 7) Hematocrit score is calculated as follows, adding to or subtracting from total score according to sign:
 - 47 minus hematocrit value for males
 - 42 minus hematocrit value for females;

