4.2 MODIFIED MAYO SCORE (ULCERATIVE COLITIS PATIENTS)

The Modified Mayo Score (excluding the Physician's Global Assessment [PGA] component) includes stool frequency, rectal bleeding, and the appearance of mucosa upon endoscopy. Stool frequency is based on a scale of 0 to 3 (0 = "normal", 1 = "1 to 2 stools/day > normal", 2 = "3 to 4 stools/day > normal", 3 = "> 4 stools/day > normal"). Rectal bleeding will be based on a scale of 0 to 3 (0 = "none", 1 = "streaks of blood", 2 = "obvious blood", 3 = "blood alone passed"). Appearance of mucosa upon endoscopy will be based on a scale of 0 to 3 (0 = "normal", 1 = "mild friability", 2 = "moderate friability", 3 = "exudation, spontaneous bleeding"). The score consists of the sum of all 3 criteria and can range from 0 to 9, with higher scores indicating more severe disease. This score will be derived programmatically for Visit 1 and Visit 10 using the Modified Mayo Endoscopic score from the central reader and self-reported data on stool frequency and rectal bleeding from 7 days prior to Visit 1 (Screening) and Visit 10 (Day 56/ET).

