5.1 BASELINE AND CHANGE FROM BASELINE MEASUREMENTS

The baseline measurement will be defined as the last non-missing assessment on the day of or prior to first study dose administration (includes all data up to the first dose administration).

Change from baseline will be calculated as:

• (value at analysis visit – baseline value)

A positive change signifies an increase in the measurement while a negative change signifies a decrease.

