5.7 HANDLING OF MISSING DATA

All efforts will be made to minimize missing data.

CD patient diary data (total stools, loose/watery stools, abdominal pain, and general well-being) used in calculating the CDAI total score will handle missing data as follows: in cases where at least 4 days of data are non-missing for a given 7-day interval leading up to the visit date, the average of the non-missing values for all days in the 7-day interval will be imputed for missing diary days. If less than 4 days of data are non-missing, then the 7-day interval will be set to missing (Henao M.P., et al, 2015). To maintain consistency, the same approach of needing at least 4 days of non-missing data for imputation will also be used for UC patient diary data (stool frequency, rectal bleeding).

Missing laboratory data will not be imputed, unless otherwise stated.

All medications with partial or missing dates recorded on the concomitant medication electronic case report form (eCRF) page will be considered concomitant unless a partial stop date clearly indicates it was stopped before the first dose of study treatment. Start and stop dates will be imputed when partial dates are present as needed to determine concomitant medications.

Table 2: Table of Imputation Rules for Missing AE and Medication Date Times

Table 2. Table	of imputation Rules for i	viissing Till and ividan	cation Date Times
		Same as	
Missing Date	Prior to	Treatment Start	After Treatment Start
Portion	Treatment	Date	Date
Day	Month and Year <	Month and Year =	Month and Year >
	Month and Year of first	Month and Year of	Month and Year of first
	treatment:	first treatment:	treatment:
	Start Day = 1	Start Day = Day of	Start Day = 1
	Stop Day = last day of	first treatment	Stop Day= last day of
	the month reported	Stop Day = $last$	the month
		day of the month	
Day and Month	Year < Year of first	Year = Year of	Year > Year of first
Define Day as	treatment:	first treatment:	treatment:
above, then:			
	Start Month = January	Start Month =	Start Month = January
		Month of first	Stop Month = Dec
	Stop Month = Dec	treatment	
		Stop Month = Dec	
Day, Month, and	To be conservative, completely missing start dates will be set to the		
Year	date of first treatment, co	empletely missing end	dates will be set to the
	date of last contact.		
Time	me Missing start times will be imputed as 00:01 (or the start time		or the start time of the
	first dose administration if AE occurred on the date of first dose		
	administration)		

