5.8 ASSESSMENT TIME WINDOWING

Most safety and efficacy assessment summaries will be based on the nominal protocol-specified assessment times. Thus, if the protocol specified Visit 3 (Day 7) visit occurs on study Day 8, it will still be summarized as a Visit 3 (Day 7), acknowledging that all visits after Visit 2 (Day 0) have a time window of ± 3 days.

The only exception is for daily diary data. The CD diary collects abdominal pain score, frequency of loose/watery stools, frequency of total stools, and general well-being, while the UC diary collects stool frequency and rectal bleeding. These will have 7-day interval

averages calculated, corresponding to the 7 days leading up to weekly visit dates. For screening data, the 7-day intervals will be relative to the date of first dose.

Unscheduled visits prior to first dose might be considered as the baseline value while post-baseline unscheduled visits will be listed only. Unscheduled visits are possible for biologic washout, clinical laboratory assessment, ECG, physical exam, pregnancy test, and vital signs.

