8.1.2 Secondary Efficacy Endpoint(s)

CD subjects only:

- Change from baseline in CDAI item and total scores at Visits 4 (Day 14), 6 (Day 28), and 8 (Day 42)
- Change from baseline in number of total stools for 7-day interval averages from Visit 3 (Day 7) to Visit 10 (Day 56/ET)
- Change from baseline in number of loose/watery stools for 7-day interval averages from Visit 3 (Day 7) to Visit 10 (Day 56/ET)
- Change from baseline in abdominal pain score for 7-day interval averages from Visit 3 (Day 7) to Visit 10 (Day 56/ET)
- Change from baseline in general well-being for 7-day interval averages from Visit 3 (Day 7) to Visit 10 (Day 56/ET)

UC subjects only:

- Change from baseline in stool frequency for 7-day interval averages from Visit 3 (Day 7) to Visit 10 (Day 56/ET)
- Change from baseline in rectal bleeding for 7-day interval averages from Visit 3 (Day 7) to Visit 10 (Day 56/ET)

• Change from baseline in Modified Mayo Score at Visit 10 (Day 56/ET)

Both CD and UC subjects:

• Change from baseline in IBD-Q total score at Visit 10 (Day 56/ET)

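### Diary averages count back 7 days from the actual visit with no cut at first dose, so an early in-window Visit 3 mixes pre-dose days into a post-baseline value

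*SAP*

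**What the plan says.** SAP 5.8 summarises most assessments at their nominal visit and names daily diary data as the sole exception. For diaries it wants 7-day "averages calculated, corresponding to the 7 days leading up to weekly visit dates". SAP 5.7 uses the same anchor for missing entries: gaps are filled with the mean of the entries present "in cases where at least 4 days of data are non-missing for a given 7-day interval leading up to the visit date", and otherwise the interval is set to missing.

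The only rule in SAP 5.8 tied to dosing concerns the run-in: "For screening data, the 7-day intervals will be relative to the date of first dose". SAP 5.1 defines baseline generally: "The baseline measurement will be defined as the last non-missing assessment on the day of or prior to first study dose administration". Neither rule says that a date before first dose must stay out of a later interval.

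Every visit after Visit 2 may move 3 days either way (protocol 12; SAP 5.8). SAP 8.1.2 treats the Visit 3 average as a post-baseline result. For UC it lists "Change from baseline in stool frequency for 7-day interval averages from Visit 3 (Day 7) to Visit 10 (Day 56/ET" and the same for rectal bleeding. For CD it lists total stools, loose/watery stools, abdominal pain and well-being in the same form.

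SAP 5.8 does not say whether the visit day itself counts. SAP 4.1 builds CDAI item 1 as the "sum of the number of loose/watery stools values recorded for the 7 days prior to the visit", and SAP 4.2 words the Mayo symptom period in a similar way.

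**The concern.** A 7-day look-back from a visit that takes place fewer than 7 days after dosing must reach back before the first dose. The entries exist: protocol 12.1.2 requires at least 7 diary days immediately before dosing. Followed as written, the plan would label a mixture of untreated and treated days as the first post-baseline reading, and the untreated days would sit on both sides of the change-from-baseline subtraction. With planned groups of 4, 4 and 6 subjects, one early attendee can visibly move a mean.

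**Working it through.** The plan gives no figure of its own here, so the check is a count of days.

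**Inputs.** First dose is protocol Day 0 (protocol 10.1). Visit 3 is Day 7 ± 3, so Day 4 to 10. The interval is 7 days with a minimum of 4 entries (SAP 5.7, 5.8). The pre-dose diary covers at least Days −7 to −1 (protocol 12.1.2). Planned groups are 4, 4 and 6 (protocol synopsis).

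**Count.** For a visit on Day d with the visit day excluded, the dates are d−7 to d−1, and pre-dose days are k = max(0, 7−d). With the visit day included, the dates are d−6 to d, and k = max(0, 6−d). Day 0 is not counted as pre-dose.

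| Visit 3 on Day | Dates, visit day excluded | Pre-dose days | Share, complete diary | Largest share with only 4 entries | Pre-dose days, visit day included |
|---|---|---|---|---|---|
| 4 | −3 to 3 | 3 | 3/7 = 42.9% | 3/4 | 2 |
| 5 | −2 to 4 | 2 | 2/7 = 28.6% | 2/4 | 1 |
| 6 | −1 to 5 | 1 | 1/7 = 14.3% | 1/4 | 0 |
| 7 to 10 | 0 to 6, up to 3 to 9 | 0 | 0 | 0 | 0 |

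All these pre-dose days lie in the week before first dose. The remaining steps exclude the visit day and assume a complete diary.

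**Effect if the pre-dose days match the baseline-week mean.** Change shown = (7−k)/7 × (post-dose mean − baseline), that is 57%, 71% or 86% of the change for Day 4, 5 or 6. With assumed values of 6 loose stools a day before dosing and 4 after, the post-dose change is −2.0, and the plan would report:
- Day 4: (3×6 + 4×4)/7 − 6 = −1.14
- Day 5: (2×6 + 5×4)/7 − 6 = −1.43
- Day 6: (1×6 + 6×4)/7 − 6 = −1.71

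**Effect if they do not match.** Suppose loose stools on Days −7 to −1 are 8, 8, 8, 8, 4, 4, 4 (mean 44/7 = 6.29), then 6 a day after dosing (again assumed values). A Day 4 visit gives (4+4+4 + 4×6)/7 = 5.14, a change of −1.14. The post-dose dates alone give 6 − 6.29 = −0.29. Here the apparent improvement is enlarged.

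**Group mean.** If all subjects have equal changes, the pre-dose days match baseline and one subject is early, the mean change is diluted by (k/7)/n. For Day 4, 5 and 6 that is 10.7%, 7.1% and 3.6% with n = 4, and 7.1%, 4.8% and 2.4% with n = 6.

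**Other visits.** The earliest in-window Visit 4 (Day 11) uses Days 4 to 10, so it has no pre-dose day. An early-termination visit on Day d = 1 to 6 has 7−d pre-dose days. There the same look-back also feeds CDAI items 1–3 and the Mayo symptom subscores.

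**The case against.** The strongest objection concerns the exact counts. SAP 5.8 does not exclude the visit day. The support comes from SAP 4.1 and 4.2, which describe scores not derived at Visit 3, and the protocol asks for the diary to be kept up to the time of Visit 2. This stands: 3, 2 and 1 are conditional, and the alternative is 2, 1 and 0. It does not remove the problem, because Day 4 and Day 5 visits are affected either way.

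It could also be said that the visit dates in SAP 5.8 are nominal. That sits badly with diary data being the exception to nominal timing, and with SAP 5.7 anchoring on the visit date.

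On consequence, the objection is largely right. The primary objective is safety, no hypothesis is tested, the primary efficacy endpoints are endoscopic, daily entries are listed, and nothing shows that anyone will attend early.

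Two further inferences are tempting but unsupported. One is that even an on-schedule Day 7 visit shares a date with baseline, because SAP 5.1 counts the day of first dose as baseline. That requires including the visit day at Visit 2 and excluding it at Visit 3. Under one consistent convention the intervals do not meet: −7 to −1 against 0 to 6, or −6 to 0 against 1 to 7. The other is the comforting inference that the overlap can only hide a benefit and never suggest one. The second worked example shows otherwise, and dilution would equally mask early worsening.

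**Conclusion.** The point holds as a minor one. Followed as written, the plan puts pre-dose days into a value labelled post-baseline whenever Visit 3 falls on Day 4 or 5, and also on Day 6 if the visit day is excluded. The shrinkage and group-mean figures rest on complete diaries and on pre-dose days that match the baseline week; without the second condition the direction of the error is not known. The exposure is one of eight weekly intervals for six descriptive secondary endpoints, plus any early-termination visit within 6 days of first dose. It is zero if no subject is seen before Day 7. No test, error rate or scheduled endoscopic result is affected.

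**What to change.** In SAP 5.8, state four things:
- Each post-baseline diary interval is the 7 calendar dates before the visit date.
- Dates before the first-dose date are treated as missing, and the 4-day minimum and imputation of SAP 5.7 apply to what remains.
- The baseline interval for the diary averages is the 7 calendar dates before the first-dose date.
- The entry for the first-dose date is used in one interval only.

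Placing that entry post-baseline is a convention. It agrees with SAP 4.1 applied at Visit 2, and protocol 12.1.2 already secures 7 earlier dates. SAP 5.1 should refer to this definition for diary data.

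Apply the same cut to CDAI items 1–3 and the Mayo symptom subscores at an early-termination visit. Treating the dates as missing and imputing keeps the CDAI sums on a 7-day scale. Leave the Visit 1 baseline of the Modified Mayo Score in SAP 4.2 as it is.

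Write the limit as a date, not a day number. SAP 5.2 numbers the first-dose date Study Day 1 and the protocol calls it Day 0. The example in SAP 5.8, "if the protocol specified Visit 3 (Day 7) visit occurs on study Day 8", is therefore an on-time visit under SAP 5.2 (7 + 1 = 8).

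The cost is a few sentences and one date condition in the programming, on data already collected. The price is some lost intervals. A Day 4 Visit 3 keeps exactly 4 dates (Days 0 to 3), so one skipped entry makes it missing. An early-termination visit on Day 1 to 3 has no valid diary interval. Early visits would also average fewer treated days than on-time ones.

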5.9 POOLING OF INVESTIGATOR SITES

Not applicable.

5.10 ADJUSTMENTS FOR MULTIPLICITY

Not applicable due to the use of descriptive statistics only.

5.11 EXAMINATION OF SUBGROUPS

Not applicable.

6. SUBJECT SUMMARIES

6.1 ANALYSIS DATASETS

6.1.1 Full Analysis Set

The Full Analysis Set (FAS) will include subjects who receive at least one dose of study drug and have a baseline and at least one post-baseline value for any efficacy variable. As a result, dosed subjects will be included in the summarization of data in the FAS population for any efficacy variable for which they have data.

6.1.2 Safety Analysis Set

The Safety Analysis Set will include all subjects who are enrolled and receive at least one dose of study drug.

6.1.3 Pharmacokinetic Analysis Set

The Pharmacokinetic (PK) Analysis Set will include all subjects who receive at least one dose of study drug and for whom plasma concentration data are available, minimally at baseline and one post-baseline visit.

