12.3.2.1. Blood Sample Collection and Analysis

Blood samples will be collected within 60 minutes prior to the administration of MDGN-002 on Days 0, 14, 28 and 42 (Visits 2, 4, 6, and 8 respectively) and at any time on Days 7, 21, 35, 49, 56, and 84 (Visits 3, 5, 7, 9, 10, and 11) and processed to plasma (see laboratory manual). Time of PK samples will be recorded in the electronic CRF. A total of 1.0mL plasma (0.5 mL per PK and ADA sample) will be collected from each subject to measure plasma concentrations of

MDGN-002 or ADA samples. Pharmacokinetic and ADA samples will be processed according to the methods and directions set forward in the Laboratory Manual(s) and guidance(s).

Pharmacokinetic and ADA plasma sample analysis will be performed by laboratory defined in the Laboratory Manual(s) and guidance(s), according to their SOPs using a validated enzyme-linked immunosorbent assay (ELISA). Assay and analysis details will be described in the method validation and bioanalytical information.

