13.1.1. Analysis Populations

The Safety Population will include all subjects who are enrolled in the study and receive any amount of investigational product. The Pharmacokinetic Population will include all subjects who received their assigned dose of MDGN-002 and for whom MDGN-002 plasma concentration data are available. The Efficacy Population will include all subjects who have a baseline and at least 1 post-baseline efficacy score.

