10. PK ANALYSIS

PK concentration data will be presented in a by-subject listing and summarized by disease, cohort and visit using continuous summaries for the PK analysis set. Continuous summaries will include arithmetic as well as geometric statistics: n, mean, standard deviation, coefficient of variation, median, minimum, maximum, geometric mean, geometric standard deviation, and geometric coefficient of variation.

Plasma concentrations that are reported as lower limit of quantification (LLOQ) will be set to 0 (zero) for reporting and summary statistics, except for geometric mean and error, for which only nonzero data is included.

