14. CHANGES TO THE ANALYSES PLANNED IN THE PROTOCOL

Not applicable.

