15. TABLE OF CONTENTS FOR APPENDICES

15.1 TABLES

Table Number	Analysis Set	Title	
14.1.1	All Subjects	Patient Disposition	
14.1.2	Safety	Important Protocol Deviations	
14.1.3	Safety	Demographics and Baseline Characteristics	
14.1.4	Safety	Prior Medications by ATC Class and Preferred Term	
14.1.5	Safety	Concomitant Medications by ATC Class and Preferred Term	
14.1.6	PK	Pharmacokinetic Concentration	
14.2.1	FAS	Simple Endoscopy Score for Crohn's Disease (SES-CD)	
14.2.2	FAS	Modified Mayo Score for Ulcerative Colitis	
14.2.3	FAS	Ulcerative Colitis Subject Diary	
14.2.4	FAS	Crohn's Disease Activity Index (CDAI) Item and Total Scores	
14.2.5	FAS	Crohn's Disease Subject Diary	
14.2.6	FAS	Inflammatory Bowel Disease Questionnaire (IBD-Q)	
14.3.1	Safety	Study Drug Exposure	
14.3.2.1	Safety	Overall Summary of Treatment Emergent Adverse Events	
14.3.2.2	Safety	Treatment Emergent Adverse Events by System Organ Class and Preferred Term	
14.3.2.3	Safety	Study Drug Related Treatment Emergent Adverse Events by System Organ Class and Preferred Term	
14.3.2.4	Safety	Treatment Emergent Adverse Events by Preferred Term	
14.3.2.5	Safety	Treatment Emergent Adverse Events by System Organ Class, Preferred Term, and Severity	
14.3.3.1	Safety	Hematology Parameters	
14.3.3.2	Safety	Chemistry Parameters	
14.3.3.3	Safety	Fecal Chemistry Parameters	
14.3.4.1	Safety	Soluble LIGHT Levels	
14.3.4.2	Safety	Tissue LIGHT Levels	
14.3.5	Safety	Vital Signs	
14.3.6	Safety	Electrocardiogram (ECG)	

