15.2 LISTINGS

Listing Number	Analysis	Title
	Set	

16.2.1.1	All Subjects	Subject Disposition
16221		Subjects Not Meeting Inclusion / Meeting
16.2.2.1	All Subjects	Exclusion Criteria
16.2.2.2	All Subjects	Protocol Deviations
16.2.3	All Subjects	Study Populations
16.2.4.1	Safety	Demographics and Baseline Characteristics
16.2.4.2.1	Safety	Medical History
16.2.4.2.2	Safety	Crohn's Disease History
16.2.4.2.3	Safety	Ulcerative Colitis History
16.2.4.3	Safety	Prior and Concomitant Medications
16.2.5.1	Safety	Drug Administration and Accountability
16.2.5.2	PK	Pharmacokinetic Sample Collection and Concentration
16.2.5.3	Safety	Anti-drug Antibodies (ADA)
16.2.6.1.1	FAS	Quantitative Endoscopy (SES-CD) and Biopsy – Part 1
16.2.6.1.2	FAS	Quantitative Endoscopy (SES-CD) and Biopsy – Part 2
16.2.6.2.1	FAS	Modified Mayo Score for Ulcerative Colitis
16.2.6.2.2	FAS	Ulcerative Colitis Subject Diary
16.2.6.3.1	FAS	Crohn's Disease Activity Index (CDAI) Scores
16.2.6.3.2	FAS	Crohn's Disease Subject Diary
16.2.6.3.3	FAS	Crohn's Disease Activity Index (CDAI) Non- Diary Item Data and Related Questions
16.2.6.4	FAS	Inflammatory Bowel Disease Questionnaire (IBD-Q)
16.2.7.1	Safety	Adverse Events
16.2.7.2	Safety	Serious Adverse Events
16.2.7.3	Safety	Adverse Events Leading to Discontinuation
16.2.8.1	Safety	Hematology Laboratory Results
16.2.8.2	Safety	Serum Chemistry Laboratory Results
16.2.8.3	Safety	Fecal Chemistry Laboratory Results
16.2.8.4	Safety	Urinalysis Laboratory Results
16.2.8.5	Safety	LIGHT and Confirmatory Disease Biopsy Results
16.2.8.6	Safety	Other Laboratory Results
16.2.9.1	Safety	Vital Sign Measurements
16.2.9.2	Safety	Physical Examination
16.2.9.3	Safety	12-Lead Electrocardiogram (ECG)

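### SAP 6.1.3 makes a pre-dose concentration a condition of entry to the PK analysis set, although the protocol states no such condition and no planned post-dose PK summary needs it

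*SAP*

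**What the plan says.** The two documents define the PK population differently.

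- Protocol 13.1.1: "The Pharmacokinetic Population will include all subjects who received their assigned dose of MDGN-002 and for whom MDGN-002 plasma concentration data are available". No particular sampling time is named.
- SAP 6.1.3: subjects with at least one dose, "for whom plasma concentration data are available, minimally at baseline and one post-baseline visit".

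The SAP's set governs every PK output it plans. SAP 10 states: "PK concentration data will be presented in a by-subject listing and summarized by disease, cohort and visit using continuous summaries for the PK analysis set". In SAP 15.1, Table 14.1.6 ("Pharmacokinetic Concentration") carries the PK set as its analysis set. In SAP 15.2, so does Listing 16.2.5.2 ("Pharmacokinetic Sample Collection and Concentration").

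SAP 14, the place for departures from the protocol's planned analyses, reads "Not applicable".

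**The concern.** A baseline requirement makes sense where the endpoint is a change from baseline. That is the case for the efficacy endpoints in SAP 8.1, and the Full Analysis Set in SAP 6.1.1 has the same structure. The PK outputs are concentrations by visit. Here the requirement can remove a subject because of a sample taken before any study drug was given, whatever the quality of the samples taken afterwards.

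Estimating plasma concentrations is a stated secondary objective, and each reporting column holds only 4 to 6 subjects. Because the listing is restricted to the same set as the table, the excluded subject's concentrations would appear in neither. The anti-drug antibody listing (16.2.5.3) uses the Safety set, so that subject's antibody results would be shown without the concentrations that help to interpret them.

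The protocol allows replacement only for subjects who withdraw before the third dose (8.7 and 9.6), so a completer excluded this way would not be replaced. Under SAP 1, analyses added after database lock to supplement the plan must be labelled post-hoc, and restoring the subject at that stage would carry that label.

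**Working it through.** **1. Samples per subject.** Protocol 12.3.2.1 schedules PK draws on Days 0, 7, 14, 21, 28, 35, 42, 49, 56 and 84. Leaving out Day 0 gives Days 7, 14, 21, 28, 35, 42, 49, 56 and 84, which is 9 post-dose samples. This reproduces the 9 samples in the general PK row of Protocol Table 3.

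**2. Can another value stand in for Day 0?** SAP 5.1 takes baseline as the "last non-missing assessment on the day of or prior to first study dose administration". Protocol 12.3.2.1 says: "Blood samples will be collected within 60 minutes prior to the administration of MDGN-002 on Days 0, 14, 28 and 42". Of these, only the Day 0 draw precedes the first dose, and none of the remaining PK days does. A missing Day 0 result therefore has no scheduled substitute.

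**3. What counts as missing?** Protocol Table 3 has a separate row for Day 0 pre-dose PK with 2 samples of 2.0 mL; antibody samples have their own row. On that plan a subject lacks a baseline only if both samples are missing or unusable. SAP 10 sets values reported at the quantification limit to zero and keeps them in the arithmetic summaries, so such a Day 0 result is data and the subject stays in.

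**4. Does any planned PK summary need the baseline?** SAP 10 lists arithmetic and geometric statistics of concentration by disease, cohort and visit. It plans no change from baseline. The Day 0 value enters only the Day 0 row.

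**5. Size if one subject is excluded.** Planned numbers are 4, 4 and 6 (Protocol synopsis), total 14.

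| Column | n | n after | Share lost | Post-dose values lost |
|---|---|---|---|---|
| CD 1 mg/kg | 4 | 3 | 1/4 = 25.0% | up to 9 of 4 × 9 = 36 |
| CD 3 mg/kg | 4 | 3 | 1/4 = 25.0% | up to 9 of 36 |
| UC 3 mg/kg | 6 | 5 | 1/6 = 16.7% | up to 9 of 6 × 9 = 54 |
| All | 14 | 13 | 1/14 = 7.1% | up to 9 of 14 × 9 = 126 |

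As a guide to precision, with the SD held fixed the standard error of a visit mean grows by √(4/3) = 1.155 in a CD cohort (about 15%) and by √(6/5) = 1.095 in UC (about 10%).

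**6. How often?** The documents give no rate of missing Day 0 results. Let p be the assumed probability that a subject has no usable Day 0 result at all, with subjects independent. The chance of at least one exclusion among n is 1 − (1 − p)^n.

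| Assumed p | n = 4 | n = 6 | n = 14 |
|---|---|---|---|
| 2% | 7.8% | 11.4% | 24.6% |
| 5% | 18.5% | 26.5% | 51.2% |
| 10% | 34.4% | 46.9% | 77.1% |

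These rows only show how the result depends on p. With two samples planned and drawn on site just before dosing, p may lie below the range shown.

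**The case against.** Several counter-arguments have force.

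- **The trigger is narrow.** A reader might infer that one lost or haemolysed pre-dose tube excludes a subject. Table 3 does not support that, because it plans two Day 0 samples. This stands, and it lowers the risk without removing it.
- **The Day 0 sample is not worthless.** A reader might infer that its value must be zero and that it tells us nothing. No section states the expected Day 0 value; zero is an inference from its being drawn before study drug. The sample can reveal assay background or unexpected earlier exposure. This stands as a reason to collect and report it. It is not a reason to discard the later samples of a subject who lacks it.
- **The SAP may simply be filling in detail.** Protocol 13 describes itself as a summary and leaves detail to the SAP, so the baseline phrase could be read as spelling out what availability means. A reader who calls this a flat contradiction of the protocol goes further than the text. Even so, the phrase narrows the population, the SAP gives it no purpose, and SAP 14 is silent.
- **The consequence is limited.** Nothing is tested (SAP 5.6) and the sample size rests on feasibility (SAP 3). SAP 1 also allows a separate PK document where needed, though nothing indicates that it would redefine the set. The first part stands and caps the importance of the point.

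**Conclusion.** The point holds in a limited form. SAP 6.1.3 adds an undeclared entry condition that serves no planned post-dose PK summary. If a dosed subject had no usable Day 0 result, up to 9 valid post-dose concentrations would leave both the PK table and the PK listing. That is 25% of a CD cohort or 16.7% of the UC group for one such subject.

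This rests on three readings: the two Day 0 samples in Table 3 are both assayable for concentration; a below-quantification result counts as available; and the post-dose samples of the affected subject are otherwise valid. The size is conditional on an event whose frequency the documents do not give.

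A reader might also infer that the rule biases the PK estimates. The documents do not support that: nothing in them links loss of a pre-dose sample to later concentrations. The expected effect is lost precision in a descriptive secondary objective, with no error rate involved. It is worth correcting because the correction is so small.

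**What to change.** Before database lock:

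1. Redefine the set in SAP 6.1.3 as subjects who received at least one dose of study drug and have at least one post-dose plasma concentration.
2. Keep collecting, listing and summarizing the Day 0 sample, so that its value as an assay and exposure check is retained.
3. Record in SAP 14 what still differs from Protocol 13.1.1: the SAP asks for at least one dose where the protocol asks for the assigned dose, and the revised set asks for a post-dose value where the protocol names no time.

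If the sponsor prefers to keep the baseline condition, SAP 14 should declare and justify it, and Listing 16.2.5.2 should cover all samples from dosed subjects.

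The cost is one phrase in SAP 6.1.3 and a short entry in SAP 14. No sampling, visit or assay changes.
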